## **Study Design and Methodology**

This is a prospective pilot study. Targeted population include patients with COPD, non-oxygen dependent, with a baseline normal bicarbonate on previous lab (within 6 months of enrollment). Patients will be randomly selected to be part of the study sample. Recruitment will occur in both inpatient and outpatient settings. An email briefly explaining the objectives of the study will be sent to Internal Medicine residents and Pulmonary Critical Care fellows to help in patients' recruitment. Patients will be enrolled in the study only after being seen by [name] or [name]. The study is expected to finish by the end of January 2017 or twelve months post IRB approval. Patients will be recruited and enrolled over six months, and the collected data will be analyzed six months after the last patient was included in the study. We will target a study sample of 30 as detailed in the statistical analysis section, where patients will be their own control (3 months without HFNC followed by 3 months with HFNC).

At the time of enrollment, demographic data, forced expiratory volume (FEV1) and a baseline PaCO2/serum bicarbonate when available will be collected. Patients will be taught how to calculate the BCSS score and will be provided with 120 photocopies of the BCSS score table (Table.1). They will be asked to complete the BCSS score every night if possible or at least 3 times per week. Patients will be followed for a total of 3 months, prior to starting home HFNC. Patients who were enrolled post COPD exacerbation will be followed for an extra month (a total of 4 months) and their BCSS scores from the first month will not be included in the statistical analysis since they will not be at their baseline at the time of enrollment. Compliance to follow up visits and completing the BCSS score will be a requirement to qualify for starting HFNC. To improve compliance, a follow up in the clinic or over the phone will take place at 6-8 weeks post enrollment.

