After 3-4 months follow-up post enrollment, patients will be brought to the clinic for HFNC education/fitting. A baseline BCSS score (BCSS0) will be completed and the mean of last 3 months' BCSS scores ( $\overline{BCSS}_{w/oHFNC}$ ) will be calculated. The number of COPD exacerbation per last 3 months with new baseline PaCO2/serum bicarbonate, if available, will be collected. The HFNC device will be set at a fixed flow of 30L/min and a FiO2 of 21% (room air). Patients will be instructed to wear HFNC as long as they can while targeting at least 6 hours/day, and to record the number of hours they wear it per day. Patients will continue to complete the BCSS score every night or at least 3 times per week. After 6-8 weeks, a follow-up appointment over the phone or in the clinic will take place.

At the end of the 3 months HFNC trial, patients will be brought back to the clinic, and a BCSS score will be completed (BCSS3) and the mean BCSS of the last 3 months ( $\overline{BCSS}_{w/HFNC}$ ) will be calculated. The number of hours/day wearing the HFNC, the number of COPD exacerbations per last 3 months, and new baseline PaCO2/serum bicarbonate (if available), will be collected.

Both the difference between the mean of baseline BCSS scores ( $\overline{BCSS}_0$ ) and the mean of BCSS scores post 3 months HFNC ( $\overline{BCSS}_3$ ), ( $\Delta 0-3 \overline{BCSS}$ ); and the difference between the means of BCSS without HFNC ( $\mu_{\overline{BCSS}_{w/oHFNC}}$ ) and with HFNC ( $\mu_{\overline{BCSS}_{w/HFNC}}$ ), ( $\Delta \mu_{\overline{BCSS}_{w/oHFNC}} - \mu_{\overline{BCSS}_{w/HFNC}}$ ) will be calculated. The difference between the means of number of COPD

exacerbation per 3 months pre and post-HFNC, and the means of baseline PaCO2/serum bicarbonate (if available) pre and post-HFNC will be calculated as well, as secondary objectives. We will also look for a possible correlation between the number of hours using home HFNC and the change in BCSS score.

Regardless of the change/or not in BCSS score, patients will be able to provide their feedback regarding the device; they will be asked how helpful it was on a scale of 0 to 3, with 0 being equivalent to “not helpful at all” and 3 corresponding to “very helpful”. Patients will be asked as well if they would like to keep/not keep the device.

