## Appendix

Table 1. The Breathlessness, Cough, and Sputum Scale (BCSS)

Permission to use this score obtained from [name] ([[contact]](mailto:[contact]))

Please complete in the evening (prior to going to bed)
Please enter day (Monday, Tuesday, etc.):
Please record the date (day/month):
How much difficulty did you have breathing today? 

▪ 0 = None: unaware of any difficulty

▪ 1 = Mild: noticeable during strenuous activity (eg, running)

▪ 2 = Moderate: noticeable during light activity (eg, bedmaking)

▪ 3 = Marked: noticeable when washing or dressing

▪ 4 = Severe: almost constant, present even when resting

How was your cough today? 

▪ 0 = None: unaware of coughing

▪ 1 = Rare: cough now and then

▪ 2 = Occasional: less than hourly

▪ 3 = Frequent: one or more times an hour

▪ 4 = Almost constant: never free of cough or need to cough

How much trouble was your sputum today? 

▪ 0 = None: unaware of any difficulty

▪ 1 = Mild: rarely caused problem

▪ 2 = Moderate: noticeable as a problem

▪ 3 = Marked: caused a great deal of inconvenience

▪ 4 = Severe: an almost constant problem

Total Score:

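### BCSS0 and BCSS3 are single scores taken at clinic visits, although the BCSS form is a bedtime form about the day, and the plan does not say what period a clinic score covers

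*Combined protocol and SAP*

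**What the plan says.** Study Design and Methodology sets up two streams of BCSS data.

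- **Diary.** In the period without HFNC: "They will be asked to complete the BCSS score every night if possible or at least 3 times per week". The same frequency continues during the HFNC period.
- **Clinic.** "After 3-4 months follow-up post enrollment, patients will be brought to the clinic for HFNC education/fitting". For that visit the plan continues: "A baseline BCSS score (BCSS 0 ) will be completed and the mean of last 3 months' BCSS scores" (the mean to be calculated), so BCSS0 is a separate score completed there. At the end of the HFNC period, "patients will be brought back to the clinic, and a BCSS score will be completed (BCSS 3").

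Two contrasts follow. One is introduced by "Both the difference between the mean of baseline BCSS scores" and compares BCSS0 with BCSS3. The other is introduced by "and the difference between the means of BCSS without HFNC" and compares the 3-month diary means without and with HFNC. The plan does not rank them. The Statistical Analysis section does not say which of them the paired t-test and the SD of 1.8 refer to.

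The form itself (Appendix, Table 1) is headed "Please complete in the evening (prior to going to bed"), and its opening item is "How much difficulty did you have breathing today". The cough and sputum items refer to the same day.

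**The concern.** The clinic scores and the instrument's instruction do not fit together. A bedtime form about the day looks back on a day that is nearly over. A form completed at an appointment is normally filled in before the day has ended. The plan gives no visit time, no instruction to score the previous day, and no rule replacing the clinic score with a diary sheet. BCSS0 and BCSS3 may therefore cover different parts of a day in the same patient.

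Each is also one score per patient. The mean of baseline scores in the plan is a mean over patients, so it does not average out a patient's good and bad days. Evening sheets that could do so are already requested on both sides of the comparison.

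BCSS change is the primary objective and neither contrast is named as primary, so the clinic-score contrast could become the headline result. If the two contrasts disagreed, appointment time or one unusual day would be a possible explanation, and the plan could not separate it from an effect of HFNC.

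**Working it through.** **1. The plan's own figure.** Inputs from Statistical Analysis: difference 1.3, SD of paired differences 1.8, alpha 5%, power 90%, dropout 25%. The test is taken as two-sided; sidedness is not stated, but one-sided versions give 17 to 18 and do not match.

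- Normal approximation: n = ((1.960 + 1.282) × 1.8 / 1.3)² = 20.14.
- With the small-sample term 1.960²/2 = 1.92: 22.07, in line with the stated 22.
- Exact noncentral t: power 89.8% at n = 22 and 91.1% at n = 23.
- Dropout: 22 / 0.75 = 29.3, so 30.

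The sample size reproduces and is not in question.

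**2. Day-to-day noise in the contrast.** Let s be the day-to-day within-patient SD. The documents do not give it; s = 0.8 to 1.5 is assumed. The two clinic days are about three months apart and are treated as independent.

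- Two single scores: √2 × s = 1.13 (s = 0.8) to 2.12 (s = 1.5).
- Two 7-evening means, independent days: √2 × s / √7 = 0.43 to 0.80.
- Two 3-evening means, independent days: √2 × s / √3 = 0.65 to 1.22.
- Two 7-evening means, AR(1) correlation 0.5 between consecutive days: the variance of a 7-day mean is s²/7 × [1 + 2 Σ(1 − k/7) × 0.5^k], k = 1 to 6. The sum is 0.717, so the factor is 2.433/7 = 0.348. The noise SD is √2 × s × √0.348 = 0.67 to 1.25.

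For scale, the target change is 1.3.

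**3. Consequence for power.** This depends on what the 1.8 describes.

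*If 1.8 is the SD of the difference between 3-month diary means* (at least 3 × 13 = 39 sheets per period, independent days), the single-score SD is √(1.8² + 2s²(1 − 1/39)):

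| s | SD, single scores | Power at n = 22 | n for 90% power |
|---|---|---|---|
| 0.5 | 1.93 | 85% | 26 |
| 1.0 | 2.28 | 72% | 35 |
| 1.5 | 2.76 | 56% | 50 |

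With 7-evening means the SD is √(1.8² + 2s²(1/7 − 1/39)): 1.86 at s = 1.0 and 1.94 at s = 1.5. Most of the loss is recovered.

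*If 1.8 already describes the difference of two single scores*, 22 patients serve this contrast as planned and no power is lost. Averaging would then give more power than stated: at s = 0.8, the 7-evening SD is √(1.8² − 2 × 0.8² × 6/7) = 1.46, with 98% power at n = 22. On this reading s cannot exceed 1.8/√2 = 1.27, so the top of the assumed range is ruled out.

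**4. Sheet supply.** The plan hands out 120 copies. Nightly use over 3 + 3 months is 26 × 7 = 182 sheets, or about 212 with the extra month for patients enrolled after an exacerbation. A nightly completer runs out at day 120, around month 4. At three per week, 3 × 26 = 78 sheets (about 91 with the extra month) are needed, and 120 suffice.

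**The case against.** The strongest reply has four parts.

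- **The scores are not shown to be part-day.** This stands as a limit. A reader might infer that both scores miss the rest of the day, but no visit time or recall period is given. The defect is that the period is undefined. A reader might also think the form cannot be answered without a full day. The cough anchors include hourly rates and the sputum anchors name no activity, so only the heading and the reference to the day support the full-day reading.
- **A clinic effect would cancel.** A constant shift from scoring in clinic does drop out of the within-patient difference, and the plan never subtracts a clinic score from a diary mean. What remains is a shift that differs between the two visits. It could go either way and cannot be sized.
- **The noise figures rest on assumptions.** They do. The day-to-day SD is assumed, and independence between days flatters averaging; the result at a correlation of 0.5 is shown for that reason. Averaging still helps there, but less.
- **The diary contrast already protects the design.** It carries out the own-control comparison with evening scores and is untouched. That limits the severity. It does not remove the point, because the plan calculates both contrasts and does not say which leads.

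A clinic score also gives a value for every patient who attends, whereas a diary window can be empty. That cost is real, and the sheet supply makes it more likely for BCSS3.

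**Conclusion.** The inconsistency between the form and the clinic scoring is in the text, and nothing in the plan resolves it. It affects the contrast of BCSS0 with BCSS3 only. Under an assumed day-to-day SD of 0.8 to 1.5, the two single scores put noise with an SD of 1.1 to 2.1 into that contrast, against 0.4 to 0.8 (independent days) or about 0.7 to 1.25 (correlation 0.5) for 7-evening means. The effect on power ranges from none, if 1.8 already describes single scores, to a fall to 56% at n = 22, if 1.8 describes diary means and the day-to-day SD is 1.5.

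A reader might infer that the trial's BCSS result is biased or that 30 patients are too few. The documents support neither. No direction of bias can be derived, the planned sample size reproduces, and the diary-mean contrast follows the form's instruction. Severity is low to moderate. It would rise if the clinic-score contrast were chosen as primary, a choice the plan leaves open and this point does not settle.

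**What to change.** In Study Design and Methodology, define BCSS0 as the mean of the evening diary scores from the 7 days before the fitting visit, all before HFNC starts, and BCSS3 as the mean of those from the 7 days before the end-of-HFNC visit. Require at least 3 scores in each window, which is the plan's own weekly minimum. State that no score completed in clinic enters this contrast.

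Completing the form at home on the evening of the visit is not an equivalent repair for BCSS0. That evening comes after the device has been fitted, so the score may no longer be a pre-treatment one.

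Hand out enough sheets for the whole study, or replenish them at the fitting visit, so that the last week is covered for patients who score nightly.

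The cost is one or two sentences and some photocopies, with no added visit or questionnaire. There are two downsides. A patient with fewer than 3 sheets in a window has no BCSS0 or BCSS3. The contrast will also partly overlap the diary-mean contrast, because the 7-day windows lie inside the 3-month periods.

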### **Eligibility Criteria**

All patients aged between the ages of 35 and 80 years old, in the inpatient and outpatient settings, carrying a diagnosis of COPD, confirmed by spirometry, with at least one COPD exacerbation in the past year, non-oxygen dependent, and having a baseline PaCO2 < 60 mmHg/or normal serum bicarbonate within the last 6 months are eligible for enrollment.

Patients will be excluded from the study if they fail to sign an informed consent, do not meet the inclusion criteria, remain oxygen dependent post COPD exacerbation, and do not meet the basic mental, physical, and educational capabilities to complete the BCSS score.

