## Introduction and Background

Over the last few years, High Flow Nasal Cannula (HFNC) has been gaining a lot of popularity in adult population. High Flow Nasal Cannula oxygen therapy consist of an air/oxygen blender, an active humidifier, a single heated circuit, and a nasal cannula. It has the potential to deliver a flow rate up to 60L/min in adults and an inspiratory fraction of oxygen (FiO2) close to 100%. Multiple mechanisms have been suggested to contribute to the clinical benefit of HFNC, including and not limited to:

- The use of small loose-fitting nasal prongs leads to enhanced patient comfort
- Heat and humidification increase water content of mucus, facilitating secretions removal, minimizing desiccation/epithelial injury, and decreasing metabolic cost/work of breathing;
- Higher nasal flow rate provides a more reliable FiO2 delivery by reducing inspiratory entrainment of room air
- Washout of upper airway dead space improves efficiency of ventilation and enhances oxygen delivery
- Generation of a positive end-expiratory pressure (PEEP) counterbalances auto-PEEP and decreases work of breathing

The use of HFNC has been limited to the inpatient setting, and mostly to intermediate care (step down) and intensive care units. It has been predominantly used in mild to moderate hypoxemic respiratory failure to delay and hopefully prevent endotracheal intubation and mechanical ventilation. A recent large, randomized, multicenter trial showed that in hypoxemic non-hypercapnic respiratory failure, HFNC has similar intubation rate to non-invasive positive pressure ventilation (NIPPV), but a lower 90 days mortality. On the other hand, the data on

HFNC use in other settings is lacking and is limited to anecdotal cases and small pilot studies. Despite this lack of strong data, HFNC has been frequently used in a variety of patients with different diseases. It has been used in acute pulmonary edema, in immunocompromised and Do-Not-Intubate patients, pre-intubation, post-extubation, during endoscopy, in sleep apnea, and even in acute COPD exacerbation.

Data on HFNC use in patients with COPD include the following:

- In a small recent study including patients with stable COPD and moderate hypercapnia (PaCO2 ~ 53mmHg), six weeks of HFNC caused a significant drop in PaCO2 (~ 8 mmHg), comparable to the drop observed with NIPPV.

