## **Objectives**

The primary objective of this study is to look for a correlation between the use of HFNC in the outpatient setting in patients with previous COPD exacerbation and the change in their BCSS score. We hypothesize that home use of HFNC will lead to a reduction in BCSS score by 1.3.

Secondary objectives include; looking for a correlation between the use of home HFNC and COPD exacerbations in a 6 month period. COPD exacerbations are defined as worsening symptoms of COPD requiring a change in baseline medications/inhalers or a steroid or antibiotic prescription. No arterial blood gases will be performed as part of the study but we will look for PaCO2/serum bicarbonate change with the use of home HFNC, when possible.

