### **Statistical Analysis**

Based on the “Breathlessness, Cough, and Sputum Scale” study in CHEST, a reduction in BCSS score of 1.3 with a standard deviation of 1.8 is correlated with a highly efficacious treatment. For this study to have a 90% power ( $\beta$ ) to detect a difference in the population means ( $\delta$ ) of 1.3 with a standard deviation of difference in the response of matched pairs ( $\sigma$ ) of 1.8, and using a paired t-test with an  $\alpha$  of 5%, we are required to enroll 22 patients. Assuming a 25% drop rate throughout the study period, we need to aim for a sample size of 30 patients.

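### Do the differing bicarbonate and PaCO2 conditions in the design and eligibility sections leave the study population undefined?

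*Combined protocol and SAP*

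**What the plan says.** The second sentence of Study Design and Methodology describes the target population as COPD patients who do not depend on oxygen, "with a baseline normal bicarbonate on previous lab (within 6 months of enrollment"). It gives no alternative route through PaCO2.

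Eligibility Criteria sets an age range of 35 to 80 years, spirometric confirmation of COPD, at least one exacerbation in the past year and no oxygen dependence. It then sets a laboratory condition: a baseline PaCO2 below "60 mmHg/or normal serum bicarbonate within the last 6 months are eligible for enrollment". The exclusions add no bicarbonate or PaCO2 limit. They refer back to the list, covering patients who "do not meet the inclusion criteria, remain oxygen dependent post COPD exacerbation", together with those who do not consent or cannot complete the score.

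The laboratory values come from existing records. Objectives states: "No arterial blood gases will be performed as part of the study". At enrolment, baseline PaCO2 or "serum bicarbonate when available will be collected". The pre/post comparison of mean PaCO2 and bicarbonate ("if available) pre and post-HFNC will be calculated as well, as secondary objectives") is a secondary item.

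**The concern.** Two sections describe the same population with different laboratory conditions, and nothing says which governs. Read literally, the eligibility section lets in a patient with a PaCO2 under 60 mmHg whatever the bicarbonate, whom the design sentence would not describe. The protocol's own background makes this look more than cosmetic. It cites a study of "patients with stable COPD and moderate hypercapnia" in which PaCO2 averaged about 53 mmHg, which is 60 - 53 = 7 mmHg under the eligibility limit. The slash before *or* is also imprecise, because it does not say outright what happens when both values are on file and point in different directions.

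If this mattered, it would affect the case mix of a 30-patient pilot, the reading of the secondary PaCO2/bicarbonate comparison, and the population to which the results apply.

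**Working it through.** **1. The two laboratory conditions side by side.** Class PaCO2 as under 60, 60 or more, or not on file (3 levels). Class bicarbonate as normal, raised, low, or not on file (4 levels). That gives 3 × 4 = 12 patterns.

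| Rule | Patterns met |
|---|---|
| Design sentence: bicarbonate normal | 3 |
| Eligibility section: PaCO2 < 60 or bicarbonate normal | 4 + 3 - 1 = 6 |
| Eligibility section only | 6 - 3 = 3 |
| Design sentence only | 0 |

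The three extra patterns are PaCO2 under 60 with bicarbonate raised, low or not on file. These are counts of patterns, not shares of patients; the documents give no prevalence.

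**2. The other reading of the slash.** Suppose bicarbonate counts only when PaCO2 is missing. The eligibility section then admits 4 (PaCO2 < 60) + 1 (PaCO2 missing, bicarbonate normal) = 5 patterns. The same three are extra, and one pattern (PaCO2 of 60 or more with normal bicarbonate) fits the design sentence only. On either reading, the PaCO2 route does not require a normal bicarbonate.

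**3. Is the design sentence a rule?** It says that the population includes such patients, and it omits age, spirometry and prior exacerbation. Applied as a rule, it would accept a 30-year-old, or a patient with no exacerbation in the past year; the eligibility section would accept neither. It was therefore not written as a full list. The eligibility section was, and its exclusions point back to its own inclusion criteria.

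**4. Does the narrower wording separate out hypercapnic patients?** No. The design sentence sets no PaCO2 limit. A patient with PaCO2 of 53 mmHg and normal bicarbonate fits both sections, so choosing between them would not settle whether the cohort includes patients whom the background would call hypercapnic.

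**5. Does any planned number depend on it?** Statistical Analysis uses a difference "of 1.3 with a standard deviation of difference in the response of matched pairs" of 1.8, 90% power and 5% alpha. Two-sided testing is assumed here, since sidedness is not stated.

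- Normal approximation: n = (1.8 × (1.960 + 1.282) / 1.3)² ≈ 20.1, so 21.
- Exact paired t-test: power 0.898 at n = 22 and 0.911 at n = 23, so the stated 22 reproduces to rounding.
- Dropout: 22 / (1 - 0.25) = 29.3, so 30 as stated.

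No input refers to PaCO2 or bicarbonate. Each patient is their own control (3 months without HFNC, then 3 with), so the baseline value by which a patient qualified is the same for both periods and cannot create a difference between them.

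**The case for a change.** The best case for a change is that the design sentence does more than omit something. It states a bicarbonate condition with its own six-month window, and that condition is narrower than the one in the eligibility section. Residents and fellows help with recruitment and could screen differently depending on which section they read. The background reports a fall in PaCO2 of about 8 mmHg with HFNC in moderately hypercapnic patients, and no significant change in another small study. Who is enrolled could therefore colour the secondary PaCO2 comparison, and the pilot is meant to inform a larger randomised trial.

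Part of this stands. The wording does differ, the slash is clumsy, and a single phrasing would read better. The rest carries little weight:

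- Residents and fellows only refer. Patients are enrolled after being seen by one of two designated clinicians, who have a full criteria list to work from.
- On the plain meaning of *or*, the case of disagreeing values is answered: either value suffices.
- The secondary comparison uses whatever values happen to be on file, with no blood gases drawn by the study. Sparse data will limit it far more than this wording.
- The value that qualified a patient is among those to be collected at baseline, so the cohort can be described from data already planned. A separate field would add little.

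**Conclusion.** This is a clerical inconsistency and needs no change to the design or analysis. The eligibility section is wider than the summary by 3 of 12 laboratory patterns. Following it as written still gives a sound paired BCSS analysis, with the planned 22 evaluable and 30 enrolled patients unchanged. No power figure, source of bias or primary conclusion turns on it.

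The conclusion rests on two assumptions: that the section headed as eligibility governs enrolment, which the structure of the document supports, and that baseline PaCO2 and bicarbonate are reported from the values collected, as a competent analyst would do when describing the sample. If the document is revised for other reasons, the two sentences can be made to agree. Which laboratory condition they should state is for the investigators, and nothing here bears on that choice.
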